12.3.2 Participant and Data Confidentiality

1617 Participant confidentiality is strictly held in trust by the participating investigators, their staff,
1618 and the Coordinating Center and their agents. This confidentiality is extended to cover testing of
1619 biological samples and genetic tests in addition to the clinical information relating to
1620 participants. Therefore, the study protocol, documentation, data, and all other information
1621 generated will be held in strict confidence. No information concerning the study or the data will
1622 be released to any unauthorized third party without prior written approval of the Coordinating
1623 Center.

1625 The study monitor, other authorized representatives of the Coordinating Center, representatives
1626 of the IRB or pharmaceutical company supplying study product may inspect all documents and
1627 records required to be maintained by the investigator, including but not limited to, medical
1628 records (office, clinic, or hospital) and pharmacy records for the participants in this study. The
1629 clinical study site will permit access to such records.
1630
1631 The study participant's contact information will be securely stored at each clinical site for
1632 internal use during the study. At the end of the study, all records will continue to be kept in a
1633 secure location for as long a period as dictated by local IRB and Institutional regulations.
1634
1635 Study participant research data, which is for purposes of statistical analysis and scientific
1636 reporting, will be transmitted to and stored at the Jaeb Center for Health Research (JCHR). This
1637 will not include the participant's contact or identifying information, unless otherwise specified in
1638 the informed consent form. Rather, individual participants and their research data will be
1639 identified by a unique study identification number. The study data entry and study management
1640 systems used by clinical sites and by JCHR research staff will be secured and password
1641 protected. At the end of the study, all study databases will be de-identified and archived at the
1642 JCHR.

1643 **12.3.3 Future Use of Stored Specimens**

1644 Permission to collect and store blood samples for future use will be included in the informed
1645 consent. With the participant's approval, blood specimens will be labeled by study ID and stored
1646 at Indiana University and the University of Minnesota for use by researchers, including those

1 **Hybrid Closed Loop Therapy and Verapamil for Beta Cell Preservation in New Onset**
2 **Type 1 Diabetes:**

3 **A Proof-of-Concept Study**

4

5 **Statistical Analysis Plan**

6 **Version 2.0**

7

8 Corresponds to Version 5.2 of the protocol

9

10

11

12

13

14

15

16

17

18

19

20

21

22

23

24

25

26

27

28 Version History

SAP Version	Author	Approver	Effective Date	Revision Description	Study Stage	Protocol Version
1.0	[name] & [name]	[name]	07May2020	Original Version	Enrollment has not started yet	4.1
1.1	[name]	[name]	17 Feb2021	Added conditions to calculate c-peptide; corrected typos	Enrollment ongoing	4.4
1.2	[name]	[name]	20 April 2021	Added condition to HCL per-protocol analysis	Enrollment ongoing	4.4
1.3	[name]	[name]	14 July 2022	Revised methods for handling skewed outcomes	Enrollment completed. Follow-up ongoing	5.2
2.0	[name]	[name]	27 September 2022	Included type of device as a fixed effect in models comparing CGM metrics between verapamil and placebo groups. Added more subgroup analyses. Replaced hospitalizations with SAEs as a safety metric.	Enrollment completed. Follow-up ongoing	5.2

29

30 [name]
I am digitally signing this document

31 Author: 2022-09-27 14:14:04:00

32 Environ Biol Fish (2007) 79:31–39

32

32

32 33

33 [name] <[name]>

33 I am digitally signing this document

34 Senior Statistician: 2022-09-27 14:45-04:00

For more information, visit www.ams.org or call [contact].

35

26 [name]

36 I am digitally signing this document

37 ICHR Project Director: 2022-09-28 15:38:04:00

37. **JKR Project Director:** _____

38

39

[name]

Digitally signed by [name]

[figure not shown]
40 Protocol Co-Chair

[name]
Date: 2022.09.28 16:09:35 -06'00'

41

42

43 Protocol Co-Chair

 30 Oct 2022

44

45

46 **1. Study Overview**

47 The purposes of this study are to

48 1) to determine if initiation of HCL therapy plus intensive diabetes management soon after
49 diagnosis of stage 3 T1D can achieve near-normalization of glucose concentrations that
50 preserves beta cell function (Cohort A and Cohort B will be combined for the analysis)
51 2) to determine if oral verapamil started soon after diagnosis of stage 3 T1D preserves beta
52 cell function (Cohort A)

53

54 There are two cohorts in this trial

55 A) body weight ≥ 30 kg
56 B) body weight < 30 kg

57

58 Randomization schedules will be separate for Cohort A and Cohort B and will be stratified by
59 site. Cohort A will be participating in a factorial design arm. Eligible participants will be
60 randomly assigned (1:1:1:1) to one of 4 groups:

61 • HCL and placebo
62 • HCL and verapamil
63 • non-HCL and placebo
64 • non-HCL and verapamil.

65

66 Cohort B will be not be assigned to verapamil due to their lower body weight. These participants
67 will be randomly assigned 2:1 to either HCL or non-HCL.

68

69 Participants assigned to HCL will receive intensive diabetes management with frequent contacts
70 by study staff with the goal of near-normalization of glucose concentrations. Participants
71 assigned to non-HCL will receive a Dexcom G6 CGM and diabetes management will follow
72 usual care.

73

74 Participants will be followed for 12 months from diagnosis, with visits timed from diagnosis at 6,
75 13, 26, 39, and 52 weeks. Participants will have a mixed meal tolerance test (MMTT) performed,
76 HbA1c measured, insulin dose (units/kg/day) recorded, CGM data uploaded, and pregnancy
77 testing performed (if indicated) at some or all of the previously noted timepoints.

78

79 Additional Procedures for Cohort A

80 Drug will be double blinded. Cohort A will have additional safety visits 1 week after initiation
81 of study drug and after each study drug dose increase.

82

83

84 **2. Consistency of Statistical Analysis Plan with Protocol**

85 Prior to the start of the study, the following secondary outcomes have been added that were not
86 specified in the protocol:

87 • Percentage of participants with peak C-peptide ≥ 0.2 pmol/ml
88 • Percentage of time sensor glucose from 70 to 140 mg/dL
89 • Percentage of participants with $\geq 70\%$ of sensor glucose values from 70 to 180 mg/dL
90 • Percentage of time sensor glucose > 140 mg/dL
91 • Total daily insulin per kg
92 • Basal: Bolus ratio

93
94 Serious adverse events has been added as a safety outcome in place of hospitalizations.

95 Otherwise, the author of this SAP has verified that the analyses described in this document are
96 consistent with the version of the protocol listed in the version history table above.

97
98 **3. Primary Statistical Hypotheses**

99 The primary outcome is the C-peptide area under the curve (AUC) in response to a 2-hour MMTT
100 at 52 weeks.

101
102 **3.1 HCL vs. non-HCL**

103 • *Null Hypothesis:* There is no difference in the C-peptide AUC in response to a 2-hour
104 MMTT at 52 weeks between HCL with intensive care and non-HCL with standard care
105 for the combined Cohort A and B population.
106 • *Alternative Hypothesis:* There is a nonzero difference in the C-peptide AUC in response
107 to a 2-hour MMTT at 52 weeks between HCL with intensive care and non-HCL with
108 standard care for the combined Cohort A and Cohort B population.

109
110 **3.2 Verapamil vs. Placebo**

111 • *Null Hypothesis:* There is no difference in the C-peptide AUC in response to a 2-hour
112 MMTT at 52 weeks between verapamil and placebo for the Cohort A population.
113 • *Alternative Hypothesis:* There is a nonzero difference in the C-peptide AUC in response
114 to a 2-hour MMTT at 52 weeks between verapamil and placebo for the Cohort A
115 population.

116
117 **4. Sample size**

118 The sample size calculation is detailed in a separate document and is summarized below. Sample
119 size was driven by the verapamil vs. placebo comparison as the test only includes participants in
120 Cohort A. The mean of the transformed C-peptide ($\log(AUC + 1)$) and the root mean square
121 error in the placebo group were assumed to be 0.315 and 0.18, respectively, based on 90% CIs
122 from prior studies (1). The corresponding geometric-like mean C-peptide value of 0.370
123 pmol/mL was calculated using the inverse transformation: $\exp(0.315) - 1$. A recent randomized
124 trial (2) found a 62% increase in mean C-peptide in verapamil compared with placebo, although

125 the total sample size was small (N=24) and confidence intervals were wide. Therefore, this
126 study assumed a smaller, 50% increase in mean C-peptide using verapamil. The expected
127 geometric-like mean C-peptide value in the verapamil arm was $0.370 \cdot 1.50 = 0.555$ pmol/mL.
128 After a $\log(x+1)$ transformation, the mean values in the control and treatment groups are 0.315
129 and 0.441, respectively, giving a treatment effect of $0.441 - 0.315 = 0.126$.

130 With these estimates, a sample size of 88 participants in Cohort A was calculated to provide 90%
131 power with a 5% two-sided type 1 error rate and a 1:1 treatment group allocation to detect a
132 verapamil vs. placebo treatment group difference assuming the true relative difference between
133 groups was 50%. To account for a 10% dropout rate, the sample size in Cohort A will be 98
134 participants.

135 A sample size of 33 participants for Cohort B was selected based on convenience. Participants
136 in Cohort B will be allocated to either HCL or non-HCL in a 2:1 treatment group allocation.
137 Thus, 131 participants are expected to be enrolled in either Cohort A or Cohort B with
138 approximately 71 participants in HCL/intensive care and 60 participants in non-HCL/standard
139 care arm. Assuming around a 10% dropout rate, an HCL/intensive care treatment effect of 50%,
140 and an upper confidence limit estimate of 0.18 for the standard deviation (same presumed
141 estimates for verapamil vs. placebo comparison), this study has 96% power to detect a significant
142 HCL/intensive care vs. non-HCL/standard care treatment group difference with a type 1 error
143 rate of 5%.

144

145 **5. Outcome Measures**

146 Primary Efficacy Outcome

147 The primary outcome is the C-peptide in response to a 2-hour MMTT at 52 weeks. This is
148 measured as the area under the stimulated C-peptide curve (AUC).

149

150 Secondary Efficacy Outcomes

151 *C-peptide*

- 152 • C-peptide AUC at 13, 26, and 39 weeks (52 weeks is primary outcome)
- 153 • Peak C-peptide during a 2-hour MMTT at 13, 26, 39, and 52 weeks
- 154 • Percentage of patients with peak C-peptide ≥ 0.2 pmol/ml at 13, 26, 39, and 52 weeks

155

156 *CGM Metrics*

157 The following CGM-derived indices will be computed over the study period for 24 hours,
158 daytime (6:00am to 11:59pm) and nighttime (midnight to 5:59am) at 6, 13, 26, 39, and 52 weeks:

- 159 • Mean glucose
- 160 • Percentage of time sensor glucose from 70 to 180 mg/dL
- 161 • Percentage of time sensor glucose from 70 to 140 mg/dL
- 162 • Percentage of patients with $\geq 70\%$ of sensor glucose values from 70 to 180 mg/dL
- 163 • Percentage of time sensor glucose > 140 mg/dL
- 164 • Percentage of time sensor glucose > 180 and > 250 mg/dL

165 • Percentage of time sensor glucose <54 and <70 mg/dL
166 • Coefficient of variation

167
168 *HbA1c*

169 Values at 13, 26, 39, and 52 weeks will include the following:

170 • Mean HbA1c
171 • Percentage of patients with an HbA1c <7.0% and <6.5%

172
173 *Insulin*

174 Values at 6, 13, 26, 39, and 52 weeks

175 • Total daily insulin per kg
176 • Basal: Bolus ratio

177
178 **5.1 C-Peptide**

179 *Area Under the Curve (AUC)*

180 The stimulated C-peptide AUC will be calculated for an MMTT if the following conditions hold:

181 • A C-peptide measurement available at 0 minutes.
182 • At least three C-peptide measurements available among the following 5 times: 15
183 minutes, 30 minutes, 60 minutes, 90 minutes, and 120 minutes.
184 • At least one C-peptide measurement available at 90 minutes or 120 minutes.
185 • No two consecutive C-peptide measurements missing.

186
187 If any of these conditions is violated, the C-peptide AUC will be treated as a missing value for
188 that visit. If it is discovered that the MMTT was completed while the participant was in closed
189 loop or while the participant was not fasting, those MMTT results will also be treated as missing
190 for that visit.

191
192 If the lab deems the C-peptide AUC value to be below the lower limit of detection (LLOD), the
193 C-peptide value will be assigned the value of $\frac{1}{2}$ of the LLOD, akin to TrialNet (3).

194
195 For each MMTT, the starting time of the MMTT will be defined as t=0 if the C-peptide value is
196 available at that time point.

197
198 The trapezoidal rule will be used to calculate the stimulated C-peptide AUC as a weighted sum
199 of the C-peptide measurements. Throughout the calculation, target times for C-peptide
200 measurements will be used (as opposed to the actual measurement times).

201
202 If the C-peptide measurement at 120 minutes is not available, the following steps will be used to
203 calculate AUC:

204 • Calculate AUC₉₀ from C-peptide measurements taken between baseline and 90 minutes
205 • Calculate AUC as AUC₉₀ \times (120/90)

206
207 *Peak*

208 This will be defined as the maximum of all C-peptide values during the MMTT, which can occur
209 at t=0. The rules for handling any missing measurements during the MMTT will be the same as
210 listed above for the AUC. Thus, peak C-peptide will be missing for a visit if and only if C-
211 peptide AUC is also missing.

212 **5.2 CGM Metrics**

213 Note that no pre-randomization CGM data are collected in this protocol (new onset patients) so no
214 baseline CGM metrics will be calculated.

215
216 Participants assigned to a non-HCL group will be provided a commercially available Dexcom G6
217 CGM. Participants who stop using a CGM or have insufficient CGM data will wear a blinded
218 Dexcom G6 for approximately 10 days at 6, 13, 26, 39 and 52 weeks. The CGM indices listed
219 above will be computed separately at each follow-up visit including all unblinded data 28 days
220 prior to the visit date and any data from a blinded sensor placed at the visit (or prior to the visit at
221 52 weeks). A minimum of 5 days (120 hours) of CGM data will be required to calculate CGM
222 indices at each visit.

223
224 For daytime (6:00am to 11:59pm) versions of the CGM metrics, at least 80 hours of data will be
225 required; and for the nighttime versions (midnight to 5:59am), at least 40 hours of data will be
226 required.

227
228 **6. Primary Analyses**

229 Primary analyses will follow the intent to treat principle. Primary outcome is C-peptide AUC at
230 the 52-week visit. The protocol window is 52-weeks from diagnosis \pm 14 days, but out-of-
231 window MMTT results will be included in the analysis if obtained within 52 weeks from
232 diagnosis \pm 42 days (Day 322-406 from the date of diagnosis). Any MMTT results outside this
233 analysis window will be excluded from the primary analysis and treated as missing data.

234

235 **6.1 HCL vs. non-HCL**

236 The HCL/intensive care versus non-HCL/standard care comparison will combine participants from
237 Cohort A and B. Comparisons for HCL versus non-HCL will be pooled over verapamil groups
238 (verapamil, placebo, neither [Cohort B]). Summary statistics appropriate to the distribution, mean
239 (SD) or median (quartiles) of log(AUC+1), will be tabulated for each treatment group at 52 weeks.
240 Boxplots, with HCL vs Non-HCL groups next to each other, will be produced for each visit.

241

242 A constrained longitudinal regression model will be constructed with log(AUC+1) as the
243 dependent variable controlling for age, time from diagnosis to randomization, verapamil group
244 (verapamil, placebo, or neither [Cohort B]), and clinical site (random effect). C-peptide values at
245 baseline, 13, 26, 39 and 52 weeks will be included in the longitudinal model which will account
246 for the correlated data from the same participant using an unstructured covariance matrix. If there
247 are convergence issues, a simpler covariance structure (e.g., autoregressive or compound

248 symmetry structure) will be used. The model specified above is equivalent to adjusting for baseline
249 as a covariate, but also has the advantage of being able to handle any cases of missing baseline.

250
251 A time by treatment (HCL) interaction will be included in the model so that different treatment
252 effects can be estimated. The treatment effect at 52 weeks from this model (point estimate, 95%
253 confidence interval (CI), and p-value) will be reported as the primary analysis results.

254
255 The log(AUC+1) transform is expected to make the residuals normally distributed, but regression
256 diagnostics will be performed to check the residuals. If the residuals have a skewed distribution
257 then robust regression using M-estimation will be used.

258
259 Missing data will be handled by the method of direct likelihood.
260

261 **6.2 Verapamil vs. Placebo**

262 The verapamil vs. placebo comparison will only include participants in Cohort A and will be
263 pooled over the HCL and usual care groups.

264
265 Summary statistics appropriate to the distribution, mean (SD) or median (quartiles) of
266 log(AUC+1), will be tabulated for verapamil versus placebo at 52 weeks.

267
268 A similar constrained longitudinal analysis will be performed controlling for HCL or no HCL as a
269 covariate.
270

271 **7. Analysis Cohorts**

272 **7.1 Intent to Treat**

273 The primary analyses will follow the intention-to-treat principle. They will include all
274 randomized participants, and data will be analyzed based on the treatment assigned from
275 randomization regardless of the actual treatment received. Unless specified, all analyses will be
276 ITT. As noted above, any data from an MMTT where it is known that the participant was in
277 closed loop at the time or the participant was not fasting will be excluded from analysis.

278

279 **7.2 Per Protocol Analyses**

280 In addition to ITT, per-protocol analyses for the primary outcome will be conducted for the
281 HCL/intensive therapy group vs. non-HCL/standard care comparison and, separately, for the
282 verapamil vs. placebo comparison. The per-protocol analysis will be limited to those with non-
283 missing 52-week visit data.

284

285 The per-protocol analysis for HCL/intensive therapy vs. non-HCL/standard therapy will include
286 HCL participants who use the HCL system at least 85% of the time over the course of the study
287 and all non-HCL participants. If it is discovered that a non-HCL participant was using closed
288 loop during the study, his/her data will be excluded from this per-protocol analysis.

289
290 The per-protocol analysis for verapamil vs. placebo will only include participants in Cohort A
291 who have taken at least 80% of the study drug (both active and placebo groups) over the course
292 of the study.

293

294 For each analysis noted above, the per-protocol analysis will not be conducted if the N for the
295 analysis is \geq 95% of the N in the primary intent-to-treat analysis.

296

297 **8. Secondary Analyses**

298 As described above for the primary analysis, comparisons of HCL versus non-HCL will include
299 cohorts A and B and will be pooled over verapamil groups. Comparisons of verapamil versus
300 placebo will be limited to Cohort A and will be pooled over HCL and usual care groups.

301

302 Descriptive summary statistics appropriate to the distribution will be given for each secondary
303 efficacy outcome listed above in Section 5 by treatment group at each visit. Corresponding
304 boxplot figures of baseline and 52 weeks, boxplot figures over time, scatterplots of baseline
305 versus 52 weeks, and histograms of baseline, 26 weeks, and 52 weeks will be constructed for
306 selected metrics.

307

308 **8.1 Formal Statistical Comparisons of Treatment Groups**

309

310 C-peptide Related Secondary Efficacy Outcome

311 Formal statistical comparisons of treatment groups will limited to C-peptide AUC at 13, 26, and
312 39 weeks (52 weeks is the primary analysis described above).

313

314 Other Secondary Efficacy Outcomes

315 Formal statistical comparisons of treatment groups for other secondary efficacy outcomes will be
316 limited to the following at 26 and 52 weeks:

317 • Mean HbA1c
318 • Total daily insulin per kg
319 • Selected overall (24 hours) CGM indices:

320 ➤ Mean glucose
321 ➤ Percentage of time sensor glucose from 70 to 140 mg/dL
322 ➤ Percentage of time sensor glucose from 70 to 180 mg/dL
323 ➤ Percentage of time sensor glucose >180 mg/dL
324 ➤ Percentage of time sensor glucose >250 mg/dL
325 ➤ Percentage of time sensor glucose <54 mg/dL
326 ➤ Percentage of time sensor glucose <70 mg/dL

327

328 Separate comparisons for HCL versus non-HCL and verapamil versus placebo will be done
329 similarly as described above for the primary analysis. Except where noted otherwise below in
330 Sections 8.3 and 8.5, the general approach for analysis of secondary outcomes will be as follows:
331 For each outcome, a constrained longitudinal model will be fit adjusting for age, time from
332 diagnosis to randomization, verapamil group (for HCL analysis), HCL group (for verapamil

333 analysis) and clinical site as a random effect. A treatment by time interaction will be included in
334 the model and treatment effects (and 95% CI) will be reported separately at 26 and 52 weeks.
335 Regression diagnostics and remedy for a non-normal distribution will be as described above for
336 the primary analysis. Missing data will be handled by the method of direct likelihood.
337
338

339 **8.2 Included Data**

340 The following analysis windows will be applied to determine which data values collected at a
341 follow-up visit will be included in the analysis. The windows indicated in the protocol are
342 expanded here so that data collected at some out of window visits may still be included. If there
343 are multiple visits with non-missing data values in the same analysis window, the one closest to
344 the target date (center of window) will be used for analysis.
345

346 These windows apply to C-peptide, HbA1c, and insulin. These do not apply to the CGM metrics
347 (see Section 5.2).
348

Visit	Protocol Target Window Range ^a	Protocol Allowable Window Range ^a	Proposed Analysis Window ^a
Week 13 (3 mo) ^b	91 ± 3 days	91 ± 7 days	91 ± 28 days
Week 26 (6 mo) ^b	182 ± 7 days	182 ± 14 days	182 ± 28 days
Week 39 (9 mo) ^b	273 ± 7 days	273 ± 14 days	273 ± 28 days
Week 52 (12 mo) ^b	364 ± 7 days	364 ± 14 days	364 ± 42 days

349 a - Days from diagnosis.
350 b - Applies to C-peptide (AUC and peak), HbA1c, and insulin.
351
352

353 **8.3 C-peptide Values**

354 The same log(x+1) transformation mentioned above for AUC values in the primary analysis will
355 be used for both AUC and peak at all time points. Note that TrialNet refers to the back-transform
356 of the mean of the log(x+1) values as the “geometric-like” mean. Treatment group comparisons of
357 C-peptide AUC at 13, 26, and 39 weeks will be taken from the same longitudinal model described
358 above for the primary analysis.
359

360 **8.4 HbA1c**

361 Analyses will utilize values from the central laboratory. Local HbA1c values will not be utilized.
362

363 **8.5 CGM Metrics**

364 The descriptive analyses described above will be done for each CGM index listed in Section 5,
365 separately for:

- 366 • Overall CGM data (24 hours per day)
- 367 • Daytime (limited to CGM readings from 6:00 am – 11:59 pm)
- 368 • Nighttime (limited to CGM readings from midnight – 5:59 am).

369
370 Boxplots and scatterplots will be limited to selected CGM metrics at each of the 3 times of the day
371 listed above.
372

373 Formal statistical comparisons of treatment groups will be done for the selected CGM indices
374 listed above and will be limited to the 24 hour versions (analysis of daytime and nighttime versions
375 will be descriptive only). Analysis will follow the method described above with three exceptions:

- 376 • The longitudinal model will not be constrained because no baseline values will be
377 available.
- 378 • The unconstrained longitudinal model will include 6 week values.
- 379 • For verapamil vs. placebo comparisons the type of CGM sensor used (Medtronic, Dexcom)
380 will be included as a covariate in the models. This covariate will be allowed to differ within
381 subject if the participant changes devices between visits. If the participant switches sensors
382 in the 28 day period used to calculate CGM metrics, data from both sensors will be used to
383 calculate metrics and the value for the sensor covariate will be set equal to the sensor which
384 contributed the most data.

385
386 It is likely that percentage of sensor values below 54 mg/dL and possible that the percentage of
387 sensor values above 250 mg/dL will have a skewed distribution. The other CGM metrics are
388 anticipated to have an approximate normal distribution. As described above for the primary
389 analysis, robust regression with M-estimation will be used to analyze skewed outcomes.

390
391 The percentage of patients with $\geq 70\%$ of sensor values from 70 to 140 mg/dL will be analyzed
392 using generalized estimating equations (GEE) logistic regressions adjusting for baseline HbA1c,
393 age, time from diagnosis to randomization. Clinical site will be treated as a repeated factor using
394 a compound symmetry covariance structure. A risk-adjusted difference and 95% confidence
395 interval for the percentages will be calculated using the method of Kleinman and Norton (4). This
396 analysis will be available cases only. There will be no imputation of missing data.

397 398 9. Interaction Analyses

399 A factorial design is being used for this study because it is believed to be unlikely that the device
400 (HCL) and drug (verapamil) would interact with each other. An interaction test will be
401 conducted to explore this assumption. This analysis will be limited to cohort A. Note that this
402 study has not been powered to detect interaction. Thus, this analysis is considered exploratory
403 and no primary conclusions about the efficacy of either HCL or verapamil will be based solely
404 on the results of this analysis. If the interaction term is significant, separate results also will be
405 reported (described below).

406 In cohort A, the same constrained longitudinal analysis model described above for the primary
407 analysis of C-peptide AUC at 52 weeks (Section 7.2) will be fit with the addition of a device by
408 drug interaction. If there is evidence for an interaction at 52 weeks ($p < 0.05$), the following
409 additional analyses will be performed:

- 410 • Baseline Characteristics

411 A separate table for Cohort A, one column for each of the 4 combinations of HCL and
412 Verapamil.

- 413 • HCL vs. non-HCL

Summary statistics for C-peptide AUC at 52 weeks will be given separately for each of the 4 treatment group combinations. Boxplots will be given for baseline, 6, 13, 26, 39 and 52 weeks with one box for each of the 4 treatment combinations at each visit. The point estimate, 95% confidence interval and p-value at 52 weeks will be given from the model described above for the HCL effect separately in the verapamil and placebo groups. The HCL effect will also be estimated separately in cohort B.

- Verapamil vs. Placebo

Analogous analyses will be performed as described in the previous bullet reversing the roles of HCL and verapamil (Cohort A only).

10. Sensitivity Analyses

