Figure. Effects of verapamil on endogenous beta cell function. **a**, **b**, Absolute values (**a**) and changes from individual baseline values (**b**) of the mixed-meal-stimulated C-peptide AUC at 0, 3 and 12 months of the trial in all subjects in the verapamil ($n = 11$) and placebo ($n = 13$) groups. Means and s.e. error bars are shown. For **a**, repeated-measures ANOVA, $F_{1,48} = 4.92$, $P = 0.0313$; 3 months: two-sided Student's t test, $t_{22} = -2.37$, $*P = 0.0270$; (ANCOVA, $F_{1,23} = 5.19$, $P = 0.0334$); 12 months: treatment difference, 0.28 nmol/L, 95% confidence interval (CI), 0.05 to 0.51, two-sided Student's t test, $t_{22} = -2.54$, $*P = 0.0186$; (ANCOVA, $F_{1,23} = 4.92$, $P = 0.0377$). For **b**, repeated-measures ANOVA, $F_{1,48} = 4.86$, $P = 0.0323$; 3 months: two sided Student's t test, $t_{22} = -2.08$, $*P = 0.0491$; 12 months: treatment difference, 35.4%, 95% CI, 0.8 to 69.9, two-sided Student's t test, $t_{22} = -2.12$, $*P = 0.0451$.

192
193

194 **The purpose of this study is to demonstrate proof-of-principle.**

195 As the tools to achieve near-normalization of blood glucose levels have been primitive to-date,
196 the ability to assess whether this approach will preserve β -cell function has been compromised.
197 The current study will be proof-of-principle, as conditions will be optimized beyond those
198 generally achievable in “real life”. To ensure success with early generations of HCL systems and
199 to encourage adherence, there will be intensive engagement with the study team, to a level which
200 may or may not be sustainable in clinical practice. The goal for sensor wear and time in HCL
201 therapy is at least 85%. If this proof-of-principle study demonstrates C-peptide preservation, the
202 next step might be a multicenter, intent-to-treat study to determine whether this approach can
203 practically be implemented in routine clinical practice. However, we recognize that the ability to
204 perform this larger study with a control group not on HCL may not be feasible in the future if
205 HCL therapy becomes standard-of-care in the coming years. We anticipate that improved
206 features with future generations of HCL technology will make it more feasible to maintain near-
207 universal automated insulin delivery functionality. Thus, in the future it may no longer be
208 possible to test our hypothesis.

209 **1.2 Potential Risks and Benefits of the Study**

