1377 verapamil vs. placebo treatment group difference assuming the true relative difference between
1378 groups was 50%. To account for a 10% dropout rate, the sample size in Cohort A will be 98
1379 participants.

1380
1381 A sample size of 33 participants for Cohort B was selected based on convenience. Participants in
1382 Cohort B will be allocated to either HCL or non-HCL in a 2:1 treatment group allocation. Thus,
1383 we expect 131 participants to be enrolled in either Cohort A or Cohort B with approximately 71
1384 participants in HCL/intensive care and 60 participants in non-HCL/standard care arm. Assuming
1385 around a 10% dropout rate, an HCL/intensive care treatment effect of 50%, and an upper
1386 confidence limit estimate of 0.18 for the standard deviation (same presumed estimates for
1387 verapamil vs. placebo comparison), this study has 96% power to detect a significant
1388 HCL/intensive care vs. non-HCL/standard care treatment group difference with a type 1 error
1389 rate of 5%.

1390 10.4 Outcome Measures

1391 C-peptide

1392 The primary outcome is the C-peptide in response to a 2-hour MMTT at 52 weeks. This is
1393 measured as the area under the stimulated C-peptide curve (AUC). AUC is computed using a
1394 trapezoidal rule, which is a weighted sum of the C-peptide values over the 120 min.

1395
1396 A variety of secondary C-peptide outcomes is planned, with randomization (± 3 days) AUC as
1397 baseline, including the following:

- 1398 • C-peptide AUC 13, 26, and 39 weeks (52 weeks is primary outcome)
- 1399 • Peak C-peptide during a 2-hour MMTT at 13, 26, 39, and 52 weeks

1400 1401 CGM Metrics

1402 CGM metrics from the Dexcom G6 and Medtronic Guardian Sensor 3 will be used to assess the
1403 level of glycemic control over the course of the study with respect to the study hypothesis that
1404 requires achieving near-normal glycemia in the intervention group and a separation between
1405 treatment groups in glycemic control. CGM metrics also will be used as secondary outcomes.

1406
1407 CGM-derived indices will be computed over the study period for 24 hours, daytime (6AM to
1408 midnight) and nighttime (midnight to 6AM), and at 6, 13, 26, 39, and 52 weeks.

- 1409 • Mean glucose
- 1410 • Percentage of sensor glucose from 70 to 180 mg/dL
- 1411 • Percentage of sensor glucose >180 and >250 mg/dL
- 1412 • Percentage of sensor glucose <54 and <70 mg/dL
- 1413 • Coefficient of variation

1414

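### Is the primary C-peptide AUC left undefined because SAP 5.1 and Protocol 10.4 give no unit and no division by 120 minutes?

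*SAP*

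**What the plan says.** Protocol 10.4 computes the AUC by a "trapezoidal rule, which is a weighted sum of the C-peptide values over the 120 min". SAP 5.1 repeats the idea: "The trapezoidal rule will be used to calculate the stimulated C-peptide AUC as a weighted sum" of the measurements, using target rather than actual sampling times. Neither subsection lists the weights, names a unit or mentions a divisor.

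SAP 6.1 models log(AUC+1) and reports the 52-week treatment effect with its 95% CI and p-value as the primary result.

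The unit appears in the sample-size text (Protocol 10.3, SAP 4). There the placebo mean of log(AUC+1) is 0.315, and its inverse is given as a concentration: "from prior studies (1). The corresponding geometric-like mean C-peptide value of 0.370" pmol/mL. The verapamil value is 0.555 pmol/mL and the planned effect is 0.126.

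Three other places bear on scale:
- SAP 8.3 applies the same log(x+1) to peak C-peptide, which is a concentration.
- The detection-limit rule in SAP 5.1 begins "If the lab deems the C-peptide AUC value to be below the lower limit of detection (LLOD), the" and so sets the AUC against an assay limit.
- The Protocol 1.1 figure legend gives the earlier adult trial's AUC result as "12 months: treatment difference, 0.28 nmol/L, 95% confidence interval (CI), 0.05 to 0.51".

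SAP 5.1 also has a rule that begins "If the C-peptide measurement at 120 minutes is not available, the following steps will be used to"; it takes the AUC over 0-90 minutes and multiplies it by 120/90.

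**The concern.** A textbook trapezoid returns concentration multiplied by time. A programmer who read only SAP 5.1 could produce pmol/mL x minutes, with values 120 times those used in planning. If the outcome were log(AUC), a constant factor would only move the intercept. With log(AUC+1) it changes the treatment coefficient itself, and that coefficient is the headline result. The estimate could then not be compared with the planned 0.126, and the assumed SD of 0.18 would no longer apply.

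The rule for a missing 120-minute sample adds a second worry. The factor 120/90 is right for an undivided area. It would overstate the result if applied to something already averaged over 90 minutes.

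**Working it through.** **Inputs** (SAP 4 and Protocol 10.3): placebo mean of log(AUC+1) 0.315; SD 0.18; 50% increase; two-sided 5%; 88 completers for verapamil; 71 and 60 randomised for HCL; 10% dropout.

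**1. Reproduce the plan's figures on the labelled scale.**
- exp(0.315) - 1 = 0.370; 0.370 x 1.50 = 0.555; log(1.555) = 0.441; 0.441 - 0.315 = 0.126.
- Verapamil, 44 per arm: 0.126 / (0.18 x sqrt(2/44)) = 3.28. Power by noncentral t is 90.1%; with 43 per arm it is 89.4%. The stated 88 for 90% power is reproduced.
- Dropout: 88 / 0.90 = 97.8, so 98.
- HCL: 71 x 0.9 = 64 and 60 x 0.9 = 54; 0.126 / (0.18 x sqrt(1/64 + 1/54)) = 3.79. Power by noncentral t is 96.4%, against 96% stated.

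**2. How much scale matters.** For the same two C-peptide levels, log(1 + 0.555k) - log(1 + 0.370k):

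| Scale | k | Placebo | Verapamil | Difference |
|---|---|---|---|---|
| Mean, pmol/mL | 1 | 0.315 | 0.441 | 0.127 (0.126 as rounded in the plan) |
| pmol/mL x hours | 2 | 0.554 | 0.747 | 0.193 |
| pmol/mL x minutes | 120 | 3.816 | 4.214 | 0.398 |

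The dependence is genuine.

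**3. Which scale the plan uses.** The inverse of log(AUC+1) is labelled pmol/mL, so the quantity inside the transform is a concentration. The number 0.370 alone would not rule out pmol/mL x hours; the unit label does. The earlier trial's nmol/L equals pmol/mL numerically and fits: its difference of 0.28 is of the same order as the planned 0.555 - 0.370 = 0.185. As an area in minutes the planned difference would be 0.185 x 120 = 22.2.

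**4. Whether the trapezoid wording fits that scale.** With samples at 0, 15, 30, 60, 90 and 120 minutes, the trapezoid weights are 7.5, 15, 22.5, 30, 30 and 15, which sum to 120. Divided by 120 they are 0.0625, 0.125, 0.1875, 0.25, 0.25 and 0.125, which sum to 1. The result is still a weighted sum, now in pmol/mL.

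**5. Whether the 120/90 rule fits.** Take values 0.30, 0.45, 0.65, 0.80 and 0.65 at 0 to 90 minutes. The area is 7.5(0.30) + 15(0.45) + 22.5(0.65) + 30(0.80) + 15(0.65) = 57.375. Then 57.375 x (120/90) / 120 = 0.6375, which equals 57.375 / 90, the mean over 0-90 minutes. The rule is coherent whether the division by 120 comes before or after the factor.

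**The case for a change.** The strongest case for a change is that a SAP should be reproducible from its own endpoint definition. Section 5.1 already goes into detail on minimum samples, target times and detection limits, so the divisor belongs beside them. A reader should not have to recover the scale from the sample-size section. The coefficient spans a threefold range (0.127 to 0.398) across readings. The 120/90 factor can also be misapplied: used on a 0-90 minute mean of 0.370 it gives 0.493, which is 33% too high, a shift of log(1.493) - log(1.370) = 0.086 for that test.

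What stands is that the two subsections omit the divisor and unit, and that the transform makes scale matter. It does not stand that the choice is open. The unit sits in the same paragraph as the planned effect, so anyone comparing a result with 0.126 has the scale in front of them. An analysis in minutes would give a placebo mean near 3.8 where the plan expects 0.315, an error that is hard to miss. The 33% error requires averaging over 90 minutes first and then applying a factor whose only purpose is to extend an area from 90 to 120 minutes.

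Some of the supporting evidence is weak. The detection-limit sentence may be loose wording about single assay values, sharing a transform with peak does not prove a shared unit, and the nmol/L figure belongs to another trial. The pmol/mL label carries the argument.

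**Conclusion.** This is a gap in wording that analysts would fill correctly from the plan's own unit. On a time-averaged concentration in pmol/mL, the trapezoid text, the 120/90 rule, the planned effect of 0.126 and both power statements (90.1% and 96.4% on recalculation) agree with one another. Sample size, power, model and missing-sample rule are unaffected. A line naming the divisor would be harmless, but it would alter no result.

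The conclusion rests on reading the pmol/mL label in Protocol 10.3 and SAP 4 as the unit of the analysed AUC. Both documents also refer to a separate sample-size document that was not available here and may state the unit directly.
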